4.10. Outcome of Interest

4.10.1. Primary clinical outcome and definition of treatment success

- Primary clinical outcome will be the individual time (days) necessary to return to play.
- Individual treatment success is defined as the possibility to return to play with the following criteria fulfilled (according to van der Horst et al., 2016):
 - absence of pain on palpation,
 - absence of pain during flexibility testing (active knee extension test and passive straight leg raise test),
 - absence of pain during strength testing (isometric force test),
 - absence of pain during and after functional testing (repeated sprint ability test and single leg bridge),
 - similar hamstring flexibility,
 - psychological readiness / athlete confidence, and
 - Medical Staff clearance.

4.10.2. Secondary clinical outcomes

Secondary clinical outcomes will be:

- individual patient's satisfaction at six months after inclusion into the study (using a scale ranging from 0 [maximum dissatisfaction] to 10 [maximum satisfaction]), and
- presence or absence of re-injury during a time period of six months after inclusion into the study (defined as sudden, sharp pain in the posterior aspect of the thigh that was initially injured, accompanied by the same objective criteria initially used for the diagnosis of acute HMC injury Type 3b).

4.10.3. Additional evaluations

In addition to primary and secondary clinical outcomes the following parameters will be evaluated and reported:

- Patient's sex, age, weight, height, and body mass index.
- Interval between injury and the first treatment (in days).
- Patient's individual training load (number of training sessions per week; duration of training sessions).

4.11. Blinding of therapists and assessors

- Therapists applying the treatments will not be blinded. This will be done because even when using coded "active" and "placebo" handpieces in a study on rESWT, blinding of therapists can only be achieved when another person prepares the device before rESWT or sham-rESWT. This, however, is almost impracticable and has not been done in any of the more than 100 studies on radial and focused ESWT listed in the PEDro database (Schmitz et al., 2015). The solution to this issue is a strict, standardized way of interaction between the therapist and the patients, irrespective of treatment allocation (as mentioned in a study by Buchbinder et al., 2002). This approach will also be applied in the present study.
- All assessments before the first treatment (baseline) and during the follow-up period will be performed by assessors blind to the intervention.

5. Follow-up and statistical analysis

- Follow-up will be the same for all study patients (outlined in detail in Section 4.10. above).
- The design of this study guarantees that there will be full compliance with the allocated treatment and, thus, no contamination of one group.

- The patient's age, gender, body mass index, sport that practices, position in the field, sporting gesture that caused the injury are potential confounding factors when treating acute HMC injury Type 3b with rESWT. Normal distribution of these data will be tested using the D'Agostino-Pearson omnibus test. In case of passing the normality test we will report mean and standard error of the mean of these variables; otherwise we will report inter-quartile ranges of these variables. Comparison between groups will be performed with Student's t test in case of passing the normality test or the nonparametric Mann-Whitney test in case of not passing the normality test.
- As outlined in Section 4.11.1. "Primary clinical outcome and definition of treatment success" above, the primary clinical outcome will be the individual time (days) necessary to return to play. The primary clinical outcome will return a single data point (number of days) for each patient. Time of return to play is not normally distributed data. Accordingly, we will report inter-quartile ranges of this variable. Comparison between groups will be performed using the nonparametric Mann-Whitney test.
- As outlined in Section 4.11.2. "Secondary clinical outcomes" above, one secondary clinical outcome will be assessment of patient's satisfaction at six months after inclusion into this study (using a scale ranging from 0 [maximum dissatisfaction] to 10 [maximum satisfaction]). This secondary clinical outcome will return a single data point (on a scale ranging from 0 to 10) for each patient, which is not normally distributed data. Accordingly, we will report inter-quartile ranges of this variable. Comparison between groups will be performed using the nonparametric Mann-Whitney test.
- As also outlined in Section 4.11.2. "Secondary clinical outcomes" above, another secondary clinical outcome will be presence or absence of re-injury during a time period of six months after inclusion into the study. This secondary clinical outcome will return a single data point ("yes" or "no") for each patient, which is not normally distributed data. Accordingly, we will report absolute and relative numbers of "yes" and "no" of this variable. Comparison between groups will be performed using Fisher's exact test.
- The probability value of less than 0.05 (p-value < 0.05) will be considered as statistically significant (Lang & Secic, 2006).
- All calculations will be performed using GraphPad Prism (version 5.00 for Windows, GraphPad Software, San Diego, CA, USA).
- All main conclusions of the study will be based on analyses of intention to treat rather than analyses of treatment. Note that there are various available methods for handling missing data in clinical trials (European Medicines Agency, 2010). In case of missing data (*i.e., in case a patient will withdraw or will be lost during the treatment or the follow-up periods*) we will determine together with the statistics experts at the Institute for

Medical Informatics, Biometry and Epidemiology (IBE) at the Ludwig-Maximilians-University of Munich (Munich, Germany) the most appropriate method for performing analyses of intention to treat. After randomization and the first rESWT or placebo treatment, no patient will be replaced.

- All efforts will be made to keep the proportion of patients lost to follow-up too small to affect the main findings of this study.
- Patient-centered care throughout this study will ensure that no patients will be lost to follow-up, or the number of patients lost to follow-up will be so small that findings would be unaffected by their inclusion.
- We will report actual probability values for all outcomes except where probability values less than 0.001 are found.
- We will avoid any retrospective unplanned subgroup analysis and, thus, “data dredging”.

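### The baseline rule in section 5 applies normality tests, means with SEM, and t or Mann-Whitney tests to nominal variables, and shows the SEM instead of the SD for age and BMI

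*Protocol*

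**What the plan says.** The protocol's section 5 (Follow-up and statistical analysis) names six variables. After age, gender, BMI and the sport practised, the sentence ends: "position in the field, sporting gesture that caused the injury are potential confounding factors". The next sentences treat all of them alike:

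- Normality check: "Normal distribution of these data will be tested using the D'Agostino-Pearson omnibus test".
- If it is passed: "In case of passing the normality test we will report mean and standard error of the mean of these variables".
- If it is not passed: "otherwise we will report inter-quartile ranges of these variables".
- Test: "Comparison between groups will be performed with Student's t test in case of passing the normality test", and Mann-Whitney otherwise.

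No exception is made for categorical variables. Later in the same section, re-injury (a yes/no variable) is to be reported as absolute and relative numbers and compared with Fisher's exact test.

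Section 4.10.3 opens with "In addition to primary and secondary clinical outcomes the following parameters will be evaluated and reported". It lists sex, age, weight, height, BMI, the interval from injury to first treatment, and training load. Sport, field position and gesture are not on that list.

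**The concern.** Of the six variables, only age and BMI are continuous. Gender is binary. Sport, position and gesture are categories without an order, so a mean, a quartile or a rank exists only after someone has assigned numbers to the categories, and a different assignment gives a different answer. Because the rule is written out, this is a method fixed wrongly and not a detail left open.

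The SEM raises a separate issue. A baseline table should show how much patients differ from one another. The SEM shows how precisely the mean is known, and it shrinks as the sample grows.

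At stake is how the baseline table can be read. Section 4.1 says that the design considers the items on baseline similarity in the DELPHI list and the PEDro scale. With 20 patients per arm, chance imbalance is plausible and readers will look at this table. The rule in section 5 is the only between-group comparison of baseline variables that the protocol specifies.

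**Working it through.** **Inputs.** 20 patients per arm (section 4.8) and a significance threshold of 0.05 (section 5). The protocol gives no figure for the baseline comparison, so there is none to reproduce. As a check on the group size, power for 75% versus 25% at 20 per arm (normal approximation) comes to 91.7%, against 91.8% in Table 3. The category counts below are assumptions for illustration, because the protocol gives none.

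**1. Nominal variables.** Take a four-category variable (A, B, C, D) with counts 8/3/6/3 in one arm and 3/8/3/6 in the other. The numbers 1 to 4 can be assigned in 4! = 24 ways.

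- Coding A=1, C=2, D=3, B=4. Means: (8×1 + 6×2 + 3×3 + 3×4)/20 = 2.05 and (3×1 + 3×2 + 6×3 + 8×4)/20 = 2.95. Pooled variance 1.208; standard error sqrt(1.208 × 2/20) = 0.348; t = 0.90/0.348 = 2.59 on 38 degrees of freedom; p = 0.014.
- Coding C=1, D=2, B=3, A=4. Means 2.65 and 2.55. Pooled variance 1.303; standard error 0.361; t = 0.10/0.361 = 0.28; p = 0.78.
- Over all 24 codings the t-test p-value runs from 0.014 to 0.78 and the Mann-Whitney p-value from 0.017 to 0.71. Eight of the 24 fall below 0.05 with either test.
- Pearson chi-square, which needs no coding: expected counts 5.5, 5.5, 4.5, 4.5 in each arm, so 4 × 2.5²/5.5 + 4 × 1.5²/4.5 = 4.545 + 2.000 = 6.545 on 3 degrees of freedom; p = 0.088.

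A milder assumed table, 2/8/6/4 versus 4/4/5/7, gives t-test p-values from 0.10 to 1.00 and Mann-Whitney p-values from 0.10 to 0.94, against chi-square 0.41. No coding of that table falls below 0.05. The p-value always depends on the code; whether it crosses the threshold depends on the table.

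**2. Does the normality test catch the misuse?** Not reliably. In simulated samples of 20 with four equally likely categories coded 1 to 4, about 70% passed the D'Agostino-Pearson test. With probabilities of 0.10, 0.35, 0.35 and 0.20, about 95% passed.

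**3. Gender.** With an assumed 14/20 versus 8/20, the Mann-Whitney p-value (no continuity correction) is 0.0597 under either coding. This equals the chi-square test with the (N−1) factor; ordinary Pearson chi-square gives 0.0565. The t test gives 0.0587. Reversing the codes changes nothing, so the comparison is sound. An inter-quartile range, or a mean with SEM, of a 0/1 variable is still a poor description.

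**4. Age and BMI.** SEM = SD/sqrt(n), so SD/SEM = sqrt(20) = 4.47 and the SEM is 0.22 SD. If the sentence in section 4.8 about fifty patients were the one that applied, with 25 per arm, the factor would be sqrt(25) = 5.0. It arises only in the branch where normality is passed, since the other branch reports the inter-quartile range. The t and Mann-Whitney p-values do not depend on which measure of spread is printed.

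**The case against.** The best defence is that nothing else in the protocol depends on this bullet. No adjustment, stratification or decision uses the baseline tests. Correct tables could be produced at reporting from the same data. An SEM labelled as such can be turned back into an SD by multiplying by sqrt(n). All of this stands, and it is why the point is minor. It does not make the rule right: followed literally, it yields figures for sport, position and gesture that carry no information.

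Four stronger readings are tempting, and the protocol does not support them.

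- A reader might infer that the comparison is meaningless for all four categorical variables. For gender it is not: neither test depends on the code.
- A reader might infer that the comparison of age and BMI is itself distorted 4.5-fold. Only the displayed spread is affected, and only when normality is passed.
- A reader might infer from section 4.10.3 that sport, position and gesture will not be collected. That section does not claim to be the complete list of collected data, section 4.9 provides for demographics and medical history at the first visit, and section 5 says these variables will be reported. The two lists differ; non-collection is not shown.
- A reader might infer that this table is all there is for judging comparability. Section 4.10.3 also promises weight, height, the interval to first treatment and training load.

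Whether to test normality first, and whether to print baseline p-values in a randomized trial at all, are matters of preference separate from this point.

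**Conclusion.** Wrong as written; severity minor. The rule is unsuitable for sport, field position and gesture, both as summary and as test. For gender only the summary fails. For age and BMI, the SEM understates patient spread by a factor of 4.5 at 20 per arm when normality is passed, and the test is unaffected. The range of p-values from 0.014 to 0.78 rests on assumed counts and shows that the result depends on the code; it does not predict what this trial will find. The primary Mann-Whitney analysis, the secondary outcomes and the sample size are not touched.

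**What to change.** Rewrite the one bullet in section 5:

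- Gender, sport, field position and causative gesture: counts and percentages per arm. If a test is kept, use Fisher's exact or chi-square test, in line with how the same section handles re-injury.
- Age and BMI: mean with SD, or median with quartiles.

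Then align section 4.10.3 with section 5, so that both name the same baseline variables.

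The cost is a change of wording in two places. No change to the sample size or to any outcome analysis is needed. If the case report form, which is not shown, already records sport, position and gesture, there is no data cost either; if it does not, up to three fields would have to be added.

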5.1. Power analysis

In the aforementioned studies by Reurink et al. (2014a) (outlined in detail in Fig. 5 above) and Bayer et al. (2017) (outlined in Fig. 6 above) the cumulative probability of resumptions of sports activity on day 35 after acute HMC injury Type 3b in professional soccer players (Reurink et al., 2014a) or recreational athletes (Bayer et al., 2017) was only respectively 20% (Reurink et al., 2014a) or 5% (Bayer et al., 2017) after treatment with a rehabilitation program (Fig. 9).

On this basis we performed a Power analysis for a percentage of 25% as well as (ii) for various other percentages (ranging between 10% and 99.9%) of patients with treatment success when treated with sham-rESWT + RP (n=20), accounting for a two sided-confidence interval of 95% (and, thus, a type-1 error rate of 5%) and a percentage of patients with treatment success when treated with rESWT + RP (n=20) of 75%. Calculations were performed using the software, Open Source Epidemiologic Statistics for Public Health (www.openepi.com). The results are summarized in Table 3 (on the next page).

Furthermore, we calculated the minimum sample size in both groups (rESWT + RP, sham-rESWT + RP) that would be necessary for detecting a difference in treatment success between the patients treated with rESWT + RP and the patients treated with sham-rESWT + RP accounting for a two sided-confidence interval of 95% and a power of 0.8. Calculations were also performed using the software, Open Source Epidemiologic Statistics for Public Health (www.openepi.com). The results are summarized in Table 4 (also on the next page).

Table 3. Power for the proposed RCT on rESWT + RP for acute HMC injury Type 3b, accounting for a two sided-confidence interval of 95% and a percentage of patients with treatment success when treated with rESWT + RP of 75%. *, calculated from data reported by Reurink et al. (2014a) and Bayer et al. (2017).

Percent of patients treated with sham-rESWT + RP with treatment success [%]	Power based on Normal approximation [%]	Power based on Normal approximation with continuity correction [%]
99.9	67.4	44.8
90	23.4	10.3
80	5.3	5.3
70	5.0	5.0
60	16.9	8.0
50	36.8	23.6
40	61.7	47.1
30	84.1	73.2
25*	91.8	84.2
20	96.6	92.3
10	99.8	99.3
0	100	100

Table 7. Sample size in the proposed RCT on rESWT + RP for acute HMC injury Type 3b, accounting for a two sided-confidence interval of 95% and a power of 0.8. The percentage of patients with treatment success when treated with rESWT + RP was set at 75 based on own experience (unpublished data). *, calculated from data reported by Reurink et al. (2014a) and Bayer et al. (2017).

		Sample size of both groups (rESWT + RP, sham-rESWT + RP) according to...		
Percent of patients with treatment success when treated with sham-rESWT + RP [%]	Kelsey et al. (1996)	Fleiss et al. (2003)	Fleiss et al. (2003) with continuity correction	
99.9	28	27	35	
90	99	98	111	
80	1095	1094	1134	
70	1221	1220	1259	
60	154	152	165	
50	59	58	66	
40	32	31	36	
30	20	19	23	
25*	16	15	19	
20	13	12	16	
10	10	8	11	

In summary, the proposed study would have a power of less than 0.8 in finding a difference in treatment success (possibility to return to play with criteria defined by van der Horst et al. [2016] fulfilled) between rESWT + RP and sham-rESWT + RP for treating acute HMC injury Type 3b if the percentage of patients with treatment success when treated with

sham-rESWT + RP would be higher than 30%. This, however, is not to be expected considering the aforementioned data by Reurink et al. (2014a) and Bayer et al. (2017) (c.f. Fig. 9). This reinforces the validity of the protocol of this study for testing efficacy and safety of rESWT + RP using the Swiss DolorClast for acute HMC injury Type 3b.

6. Patient protection procedures

6.1. Procedures in the event of Adverse Events

- Potential unwanted side effects of rESWT may be petechial bruises of the skin at the location of application of rESWs and temporary numbness. These unwanted side effects normally vanish within one or two days.
- Should any unwanted side effects persist for longer than usual, the investigators will treat these patients according to usual standard of care of the institution.

6.2. Procedures in the event of Emergency

The Principal Investigator is responsible for ensuring that procedures and expertise are available to cope with medical emergencies during the study.

6.3. Procedures in the event of Pregnancy

A patient must be instructed to inform the Principal Investigator if she becomes pregnant during the study. As pregnancy is a contraindication for treatment with rEWST, the patient will be terminated from the study. The investigator will follow up the pregnancy until the outcome is known.

6.4. Patient data protection

Patients' anonymity will be maintained and confidentiality of records and documents that could identify patients will be protected. Patients will only be identified by their assigned identification number on all CRFs and other records and documents. The Principal Investigator will keep a Patient Identification List with complete identification information (name, address, contact number) on each patient. Documents not for submission to the Ethics Committee of the Universidad Abierta Interamericana (Buenos Aires, Argentina), such as patient's written informed consent form, will be maintained by the Principal Investigator in strict confidence.

Monitors and auditors from the Argentinean National Administration of Drugs, Food and Medical Technology (Administración Nacional de Medicamentos, Alimentos y Tecnología Médica ([ANMAT](#)), [name]) or other regulatory agencies, will be granted direct access to patients' medical

records and other study documents for verification of study procedures and data without violating the confidentiality of the patient. The patient should be informed that by signing a written informed consent form, the patient is authorizing such access. All electronic data processed at ANMAT will be identified by patient numbers only, thereby ensuring that patients' identity remains unknown to ANMAT.

6.5. Insurance

With respect to any liability directly or indirectly caused by the investigational products in connection with this study, the Principal Investigator assumes liability by law for possible injury to the patients. Every effort will be made to achieve that (i) the Principal Investigator and his staff will follow the instructions of the manufacturers of the Swiss DolorClast device in accordance with this protocol and any amendments thereto, and (ii) the Principal Investigator and his staff will in general perform this study in accordance with scientific practice and currently acceptable techniques and know how.

6.6. Rescue medication/procedure

rESWT and RP themselves do not require specific rescue medication / procedures.

7. Study Termination/Suspension

The Principal Investigator holds the right to suspend or terminate patient's participation in this study in the event of deterioration of clinical condition at the discretion of the Principal Investigator.

7.1 Patient Withdrawal & Drop-out

Patients are free to withdraw from this study at any time for any reason.

Patients may also be withdrawn from this study at any time at the discretion of the Principal Investigator. Should a patient withdraw or is withdrawn, every effort will be made to complete and report the observations as thoroughly as possible. Possible reasons for withdrawal will be documented. For e.g.:

- adverse event(s),
- abnormal laboratory values,
- improvement of patient's condition such that he/she no longer requires study treatment,
- insufficient therapeutic effect,
- protocol violation (eg. incorrectly enrolled or randomised),
- patient requires use of unacceptable concomitant medication,
- patient not compliant with protocol procedures,

- patient develops a condition during the study that violates the inclusion/exclusion criteria,
- lost to follow-up,
- death, and
- any other reason, in the Principal Investigator's opinion, that would impede the patient's participation in the study.

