4.8. Randomization and blinding of patients

- Patients that fulfill the inclusion criteria and do not fulfill any of the exclusion criteria will be randomly allocated to either rESWT + RP (n=20) or sham-rESWT + RP (n=20).
- Randomization will be performed as described by Rompe et al. (2008) in a randomized, controlled study on rESWT for Achilles tendinopathy. Specifically, a computerized random-number generator will be used to formulate an allocation schedule. Patients will be randomized to either treatment (rESWT + RP or sham-rESWT + RP), with use of the method of randomly permuted blocks. The randomization scheme will be generated with the use of the website, www.randomization.com. Fifty patients will be randomized into five blocks. A medical assistant at the clinic of the Principal Investigator will allocate interventions by means of opaque sealed envelopes that will be marked according to the allocation schedule. The medical assistant will be unaware of the size of the blocks.

- The randomized intervention assignment as outlined above will be concealed from both patients and health care staff until recruitment will be complete and irrevocable.
- Patients will be blinded in this study.
- The assessor will be blinded in this study. The assessor is the person who will assess the outcome of treatment during follow up. In this study, the assessor will be a medical assistant at the clinic of the Principal Investigator.
- The therapist will not be blinded in this study. The therapist is the person who will administer either rESWT or sham-rESWT to the patient. In this study, the therapist will be the Principal Investigator ([name]).

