7.2. Procedures for handling withdrawal

Patients who withdraw or are withdrawn from this study will have the below information recorded:

- The reason(s) for their withdrawal
- Presence of any AEs and if so will be followed up by regular scheduled visits, telephone contact and correspondence until satisfactory clinical resolution of AEs is achieved.
- At least one follow-up contact (scheduled visit, telephone contact, correspondence) for safety evaluation during the 30 days following the last session of study treatment.
- In the event of pregnancy, the patient should be monitored until conclusion of the pregnancy and the outcome of pregnancy reported.

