10.6. Potential unwanted side effects

Potential unwanted side effects of rESWT may be petechial bruises of the skin at the location of application of rESWs and temporary numbness. These unwanted side effects normally vanish within one or two days. In case of petechial bruises of the skin at the location of application of rESWs they will be photographed and documented in the patient's record. Temporary numbness will also be documented in the patient's record. In the exceptional case that these unwanted side effects would really persist for longer than one or two days, (i) the corresponding patient would no longer be treated with rESWT or sham-rESWT but would be kept in the study for follow-up analysis, (ii) petechial bruises would be treated with, e.g., ice until they disappear, and (iii) patients with persistent numbness would be presented to a neurologist.

11. Statement on Confidentiality

All data collected from participants will not have any personal identifiers. They will instead be given a specific research ID to respect the privacy and confidentiality of participants. The Principal Investigator will keep a separate Patient Identification List with complete identification information (name, address, contact number) and randomization number on each patient. All data collected will be stored in a computer that is protected by a password at the clinic of the Principal Investigator. Only investigators and study team members will have access to the study data. This limits the access to study data to the minimum number of individuals necessary for quality control, audit and analysis. Participants will not be given access to any personal information and study data collected during this study.

12. Data Protection

All data collected will be stored in a computer that is protected by a password at the clinic of the Principal Investigator. Only investigators and study team members will have access to the study data. Study data will be stored for a duration of five years after completion of this study. All data will be destroyed thereafter.

13. Publication Policy

The investigators shall have the right to publish or permit the publication of any information or material relating to or arising from this study. All study data will be reported in a collective manner without any personal identifiers to protect the confidentiality of the participants.

14. Conflict of Interest

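### Sections 7 to 7.2 permit the unblinded Principal Investigator to withdraw patients from the study for reasons tied to recovery, and then require only safety follow-up, so outcomes may be lost in an outcome-dependent way.

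*Protocol*

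**What the plan says.** **Who may withdraw patients, and from what.** Protocol Section 7.1: "Patients may also be withdrawn from this study at any time at the discretion of the Principal Investigator". The object is the study, not the study treatment. Section 7 likewise gives the Principal Investigator the right to "terminate patient's participation in this study in the event of deterioration of clinical condition".

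**For what reasons.** Section 7.1 gives a list of possible reasons to be documented, marked as examples. Two describe the course of recovery: "improvement of patient's condition such that he/she no longer requires study treatment" and "insufficient therapeutic effect".

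**Who decides.** Section 4.8: "The therapist will not be blinded in this study", and "In this study, the therapist will be the Principal Investigator". The person with discretion over withdrawal therefore knows each patient's arm.

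**What is collected afterwards.** Section 7.2 asks for the reason, follow-up of adverse events, at least one contact "for safety evaluation during the 30 days following the last session of study treatment", and pregnancy follow-up where relevant. It names neither return to play, nor re-injury, nor satisfaction. Section 7.1 adds a general undertaking to complete and report the observations as fully as can be done.

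**What other sections say.** Section 5 states that follow-up is identical for all patients and that the main conclusions rest on intention to treat. Section 10.6 says that a patient whose sessions are stopped for persistent bruising or numbness "would be kept in the study for follow-up analysis".

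**The concern.** The primary outcome (Section 4.10.1) is the number of days to return to play. Improvement and insufficient effect are levels of that outcome, so a withdrawal for either reason depends on the quantity being compared. The decision lies with someone who knows the allocation, so the dependence could differ between arms without any intent.

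If the patient then leaves the study, no section requires the return-to-play date, the six-month re-injury status or the satisfaction score. The planned Mann-Whitney test needs one number per patient and has no natural place for a patient whose recovery was not observed. With 20 patients per arm, a handful of such gaps can matter. Section 5 leaves the missing-data method to be chosen later. That is a question of analysis; the point here is that the outcome may never be collected.

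**Working it through.** **1. Timing.** Section 4.9 gives the sessions as D5 to D23. One contact within 30 days of a last session on D23 falls by 23 + 30 = D53. The protocol (Fig. 5 legend) quotes return-to-play times from 14 to 105 days in a cited trial, so the slowest could fall 105 − 53 = 52 days after the last required contact. Re-injury and satisfaction are due six months after inclusion (Section 4.10.2), well beyond D53 in every case.

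**2. Which outcome each reason threatens.**

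| Reason for leaving | Return to play | Six-month re-injury and satisfaction |
|---|---|---|
| Improvement | Often at or near return to play already; the date may be known | At risk |
| Insufficient effect | At risk | At risk |
| Deterioration (Section 7) | At risk | At risk |

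**3. The plan's own figure.** The power table uses all 20 patients per arm, with 75% against 25% success. With pooled proportion 0.5:

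- null standard error: √(2 × 0.5 × 0.5 / 20) = 0.158
- alternative standard error: √((0.75 × 0.25 + 0.25 × 0.75) / 20) = 0.137
- power: Φ((0.50 − 1.96 × 0.158) / 0.137) = 91.7%, against 91.8% stated

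The figure reproduces. It contains no allowance for patients whose outcome is not observed.

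**4. Worst-case illustration.** The documents give no expected number of withdrawals, so everything here is assumed: 20 per arm, no true effect, log-normal return-to-play times with median 42 days and log-SD 0.5, rounded to days, two-sided Mann-Whitney test at 0.05, 10,000 simulated trials per row. The slowest *k* active patients are withdrawn and the sham arm is complete. The entries are significant results favouring rESWT.

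| *k* withdrawn, active arm only | Omitted from the test | Given the worst rank |
|---|---|---|
| 0 | 2.3% | not applicable |
| 1 | 4.8% | 2.1% |
| 2 | 8.1% | 1.5% |
| 3 | 12.0% | 0.7% |

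The worst-rank column comes from a separate run. Repeat runs of the omission column agree to within about one percentage point.

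**5. Sensitivity of the illustration.**

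- The test uses ranks, so the assumed distribution hardly matters. Log-SD 0.4 gave 2.3%, 4.7%, 8.0% and 12.0%; uniform data gave about 2.5%, 4.1%, 7.7% and 11.5%.
- The one-sided pattern matters a great deal. Removing the slowest 1, 2 or 3 from both arms gave about 3.0%, 4.5% and 4.2%.
- The handling matters as much: worst-rank assignment removes the inflation altogether.

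**The case against.** The strongest reply is that Section 7.1 is a documentation list, not a removal rule. Its items are examples, they mix patient-initiated and investigator-initiated exits, and they include loss to follow-up and death. A reader might infer that recovery itself determines who leaves. The text does not say so: it permits withdrawal and does not require it.

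Other text also points towards full follow-up. Section 5 promises the same follow-up for all and every effort to keep losses small. Sections 4.5 and 4.9 run rehabilitation for eight weeks whatever the time to return to play, and Section 4.9 gives each subject nine sessions. Section 7.1 itself undertakes to complete the observations of withdrawn patients, and Section 5 foresees withdrawals within the intention-to-treat analysis.

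A reader might also infer that withdrawal for improvement costs the primary outcome as much as withdrawal for insufficient effect. That is not supported: with three clinic visits a week, a patient well enough to need no further sessions may already be at or near return to play.

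All of this stands as a limit on the claim, but it does not close the gap. The undertaking in Section 7.1 names no outcome and no end date, and the specific list in Section 7.2 covers safety only. The contrary text shows that the withdrawal sections are out of line with the rest of the plan, which is the reason to reconcile them.

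**Conclusion.** The point holds as a conflict in the protocol. Sections 7 to 7.2 permit an unblinded person to end study participation for outcome-related reasons and then require safety data only. Section 5 calls for uniform follow-up and intention to treat, and Section 10.6 keeps patients in follow-up after sessions stop. The main exposure is return to play in slow recoverers, and six-month re-injury and satisfaction in anyone withdrawn.

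The rise from about 2% to 5%, 8% and 12% shows a mechanism, not an expected size. It rests on three assumptions that the documents do not supply: the very slowest patients leave, they leave the active arm alone, and they are omitted from the test. It would be wrong to infer that analysis could never repair such losses, since worst-rank assignment avoids the inflation in this very scenario. It would also be wrong to infer that the investigator intends, or is likely, to use the discretion selectively; nothing in the protocol says so. What no analysis can do is recover a date or a re-injury status that was never collected.

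**What to change.** Reconcile Sections 7, 7.1 and 7.2 with Sections 5 and 10.6 by adding a statement such as:

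> Stopping study sessions, for any reason, does not end study follow-up. Every randomized patient who does not withdraw consent is followed by the blinded assessor until return to play, and to the six-month visit for re-injury and satisfaction, however many sessions were received.

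Add these three outcomes to the items that Section 7.2 requires after sessions stop. Section 6.3, which also words an end of treatment as leaving the study, needs the same alignment.

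Leave the grounds for stopping treatment unchanged. In particular, the deterioration clause in Section 7 need not be deleted, because it protects patients and the problem lies only in what happens to follow-up afterwards.

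The cost is small: a few sentences, and continued contacts with the few patients who have stopped sessions, at visits that the protocol already schedules.
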